2.2.1 Participant classification

Patients may be excluded from the analysis populations defined above based on the protocol deviations entered in the database and/or on specific subject classification rules defined in [Table 2.2-1](#).

Table 2.2-1 Subject classification based on protocol deviations and non-PD criteria

Analysis set	Protocol deviations leading to exclusion	Non protocol deviation leading to exclusion
--------------	--	---

FAS	No written informed consent	Not applicable
Safety set	No written informed consent	No dose of study medication
Cross-over Set	Cross-over specific ICF not completed	Not applicable
Re-treatment Set	Re-treatment specific ICF not completed	Not applicable
PK Analysis Set	No written informed consent	No evaluable PK concentration at baseline or post-dose.

2.2.2 Withdrawal of Informed Consent

Any data collected in the clinical database after a subject withdraws informed consent from all further participation in the trial, will not be included in the analysis. The date on which a patient withdraws full consent is recorded in the eCRF.

Death events may be used in the analysis if captured from public records (registers), local law and subject informed consent permitting.

Additional data for which there is a separate informed consent, e.g., PK, biomarker etc., collected in the clinical database without having obtained that consent will not be included in the analysis. These data will be excluded by the presence of the appropriate protocol deviation criterion.

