In accordance with the recently finalized guidance for industry on considerations for the inclusion of adolescent patients in adult oncology clinical trials and the consensus expert opinion presented by the European multi-stakeholder platform ACCELERATE to include adolescents in adult oncology clinical trials when the histology and biologic behavior of the cancer under investigation is the same in, or the molecular target of the drug is relevant to, cancers in both adult and adolescent patients (FDA guidance), this study will include adolescents ≥ 15 years and >40 kg BW. Even though the number of adolescents ≥ 15 years fulfilling the inclusion criteria for this study is very small, the high unmet medical need in this population is justifying their enrollment. It is not

expected that adolescents below the age of 15 years will present with the disease meeting the inclusion criteria for this study.

Due to the radioactive nature of Lutathera and its method of infusion, and similarly to the NETTER-1 trial design, it is not possible to implement a fully double-blinded design for this study, however a central, blinded, real-time IRC (Independent Review Committee) assessment is implemented to ensure an independent evaluation of the tumor response according to RECIST 1.1 criteria.

Randomization will be stratified by Grade (G2 vs G3) and tumor origin (pNET vs other origin), preventing imbalance between treatment groups for known factors that influence prognosis.

For this trial a 2:1 randomization design is chosen to allow patients to have a higher chance of getting the treatment which is anticipated to be more effective. For the same reason and to minimize the possible higher drop-out rate in the control arm, patients will be offered to cross-over to Lutathera after centrally confirmed RECIST progression (or locally confirmed if it occurs after Week 72 post the primary end point analysis).

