2.1.1.11 Windows for multiple assessments

For the definition of time windows for visits please refer to the study protocol, [[Tables 8-3](#)] and [[Table 8-4](#)]. Variations of ± 1 week in the visits schedule are allowed.

Time windows will be defined for descriptive summary of PRO data by visit and longitudinal data analysis. If more than one assessment is available in the same time window, the assessment closest to the planned date will be considered. If two assessments are obtained equidistant compared to the scheduled visit day, the assessment obtained prior to visit will be considered.

Table 2.1-1 Time Window for PROs

Time Window	Planned Visit Timing	Time Window Definition
On treatment		
Baseline	On or before Study Day 1*	\leq Study Day 1*
Week 12	Study Day 78	Study Days 2 – 120
Week 24	Study Day 162	Study Days 121 – 204
Week 36	Study Day 246	Study Days 205 – 288
Every 12 weeks thereafter		
Week 12^*k ($k = 4, 5, \dots$)	$d = 7^*(12^*k-1)+1$	Study Days $d-41$ to $d+42$ Note: window for last visit before EOT: $d-41$ to EOT date-1

End of treatment during randomized treatment period

End of treatment	N.A.	Data collected under EOT visit
* Study Day 1 = randomization date		

Data from all assessments (scheduled and unscheduled), including multiple assessments, will be listed.

Last contact date

The last contact date will be derived for patients not known to have died at the analysis cut-off using the last complete date among the following:

Table 2.1-2 Last contact date data sources

Source data	Conditions
Date of Randomization	No Condition
Last contact date/last date patient was known to be alive from Visit Form 3	Patient status is reported to be alive
Start/End* dates from drug administration record	Non-missing dose. Doses of 0 are allowed.
End of treatment date from end of treatment page	No condition.
Date of PRO assessment	At least one non-missing answer to questionnaire
Tumor (RECIST) assessment date	For non-target lesion: non-missing lesion status; For target lesion: non-missing lesion diameter; For new lesion: "Is there a new lesion?" = yes
Laboratory/PK collection date	Sample collection marked as 'done'.
Vital signs and ECG date	At least one non-missing parameter value
Performance Status date	Non-missing performance status
Start/End dates of AE	Non-missing verbatim term
Concomitant medication/Non-drug therapy date	Non-missing medication
Physical exams	At least one non-missing value

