2.7.3 Handling of missing values/censoring/discontinuations

Time to second progression (PFS2)

The rules for censoring and event for PFS2 are summarized in [Section 2.7.1](#).

Overall Survival (OS)

If a patient is not known to have died at the time of analysis cut-off, then OS will be censored at the date of last known patient was alive, i.e., last contact date (see [Table 2.1-2](#)).

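### Register deaths after consent withdrawal can count in overall survival but register evidence of being alive cannot, so OS censoring depends on the outcome wherever registers are used

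*SAP*

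**What the plan says.** SAP 2.2.2 sets the general rule: "Any data collected in the clinical database after a subject withdraws informed consent from all further participation in the trial, will not be included". It then makes one exception: "Death events may be used in the analysis if captured from public records (registers), local law and subject informed consent permitting". No matching exception covers a register that shows the patient alive.

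The OS censoring rules are elsewhere. For a patient not known to have died, SAP 2.7.3 says "then OS will be censored at the date of last known patient was alive, i.e., last contact date". SAP 2.1.1.11 says that this date "will be derived for patients not known to have died at the analysis cut-off using the last complete date" among the sources in Table 2.1-2. The direct alive-status entry there is "Last contact date/last date patient was known to be alive from Visit Form 3"; the rest are other trial records. No public register is listed. The same section bars the cut-off date as last contact unless the patient was seen or contacted that day.

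Protocol 9.1.2 forbids further contact after withdrawal unless safety findings require it. Protocol 12.5.2 censors OS at the latest date known alive and does not restrict the source. SAP section 4 reports no change from the protocol's analyses.

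On the arms, Protocol 4.1 offers cross-over partly "to minimize the possible higher drop-out rate in the control arm".

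**The concern.** Two withdrawn patients with the same history are treated differently according to what happens next. If the register shows a death, the patient is followed to that death and counted as an event. If it shows none, the patient leaves the risk set at the last contact before withdrawal. Follow-up after withdrawal therefore exists only for those who die, and the survivors' time at risk is lost.

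That makes censoring depend on the outcome even if withdrawal has nothing to do with prognosis. The estimated hazard is too high and survival too low in any arm where it happens. If the arms withdraw at different rates, the OS hazard ratio is also distorted.

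The planned cross-over adjustments do not repair this. In SAP 5.4.3 the inverse-probability-weighted model takes the censoring time as independent of the death time, and the rank-preserving model takes it as independent of randomization. The distortion would also be hard to see, because the OS censoring reasons in SAP 2.7.1 are only alive or lost to follow-up, with no category for withdrawal.

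**Working it through.** **The plan's own figure.** The only design calculation is for PFS, and it reproduces. Events = (1.960 + 1.282)² / [(2/9) × (ln 0.5)²] = 98.4, rounded up to 99. Critical HR = exp(−1.960/√(99 × 2/9)) = 0.658, and 15/0.658 − 15 = 7.8 months. The plan states no figure for OS or for withdrawal, so the size below rests on assumptions.

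**Inputs from the documents.** 2:1 allocation; accrual 22.2 months (SAP section 3); OS follow-up to at least 48 months after the last randomization (SAP 1.1).

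**Inputs assumed.** Exponential OS with median 30 or 45 months; withdrawal unrelated to prognosis and spread evenly over months 0–24; control withdrawal 10, 15 or 20%, with half that on Lutathera; all register deaths found; true HR 1.00.

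**Person-time check.** With constant hazard λ, the estimated hazard is deaths divided by person-time. Full capture leaves the deaths unchanged and removes survivors' time after withdrawal.

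- Mean follow-up F = 48 + 22.2/2 = 59.1 months. Take withdrawal at its mean, w = 12, so F − w = 47.1.
- S = exp(−λF) is the proportion alive at F; P = (1 − S)/λ is mean person-time.
- With withdrawal proportion p, the share of person-time lost is L = p × S × (F − w)/P.
- Apparent HR = (1 − L for control)/(1 − L for Lutathera).

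Median 30: λ = 0.0231, S = 0.255, P = 32.2, so L = 0.373p. Median 45: λ = 0.0154, S = 0.402, P = 38.8, so L = 0.488p. For example, at median 45 with 15%/7.5%: (1 − 0.0733)/(1 − 0.0366) = 0.962.

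| Withdrawal, control/Lutathera | Median 30 | Median 45 | Simulated Cox HR |
|---|---|---|---|
| 10% / 5% | 0.981 | 0.975 | about 0.98 |
| 15% / 7.5% | 0.971 | 0.962 | about 0.96–0.97 |
| 20% / 10% | 0.961 | 0.949 | about 0.95–0.96 |

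The last column comes from 600,000 simulated patients per scenario under the same assumptions, and agrees.

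**Variations (simulated).**
- True HR 0.80 becomes about 0.76–0.79 over the same withdrawal patterns.
- Equal withdrawal (15%/15%): the HR is essentially unchanged.
- Reversed (7.5% control, 15% Lutathera): 1.00 becomes about 1.03–1.04.
- Half of the register deaths found: the shift is roughly halved. None found: no shift.
- Wider gaps, with exponential withdrawal and control medians of 36 or 60 months: 15%/5% gives 0.94–0.96 and 25%/10% gives 0.90–0.92.
- At the primary-analysis cut-off with full capture, HR shifts are about 0.01–0.05.
- Survival at 36 months with 15% withdrawal: about 0.50 becomes 0.485 (median 36), and 0.66 becomes 0.645 (median 60).

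**Remedies (simulated).** Censoring everyone at withdrawal returns the true HR within simulation error. So does using register deaths and register alive status together when both are confirmed. Treating every searched patient without a recorded death as alive to cut-off does not. At 15%/7.5% and half capture it gives about 1.04, whereas the SAP rule gives about 0.98.

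**The case against.** **The protocol does not predict the arm.** A reader might infer that the protocol expects more withdrawals in control, so that the bias must favour Lutathera. Protocol 4.1 calls higher control drop-out only possible and does not mention consent withdrawal. Protocol 9.1.1 says that patients who stop treatment are not withdrawn unless they withdraw consent. Section 9.1.2 defines withdrawal narrowly, including a request to stop use of data. The design's 15% dropout is a single figure, not split by arm. This objection stands: the direction is conditional.

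**Nothing is expressly discarded.** A reader might infer that the SAP orders alive evidence to be thrown away. The exclusion in 2.2.2 concerns the clinical database, and Protocol 12.5.2 would accept any date known alive. That softens the charge but does not answer it. The SAP's only exception is for deaths, its source list has no register, and its cut-off-date rule closes the remaining route.

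**The exception is narrow.** Local law and consent must permit it, so capture may be low and the full-capture figures are an upper bound for a given withdrawal pattern. This stands. Those conditions also explain part of the permissive *may*, but they do not fix what happens where use is permitted.

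**The consequence is small.** OS is estimated, not tested in the hierarchy, and cross-over and re-treatment already complicate it. With an assumed 130–165 deaths, SE(log HR) = √(4.5/deaths) is about 0.17–0.19, so a shift of 0.03 is under one-fifth of a standard error. This limits the severity, but the bias is systematic and avoidable.

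**Conclusion.** The point holds in a limited form. Where registers are used, the stated rules make OS censoring of withdrawn patients depend on whether they died. Survival is understated in both arms. The hazard ratio is distorted only if withdrawal differs by arm, in a direction set by which arm withdraws more.

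Under assumed control withdrawal of 10–20%, double the Lutathera rate, with full capture, a true HR of 1.00 becomes about 0.95–0.98. A wider gap between arms enlarges the shift, partial capture shrinks it, and no capture removes it. None of these rates is in the documents.

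The documents do not support a claim that OS is biased toward Lutathera as planned, or that any type I error claim is affected: OS is a secondary endpoint outside the hierarchy in SAP 2.6.1. The rule should be corrected because the OS hazard ratio and its confidence interval will be reported and the repair is cheap.

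**What to change.** Before database lock, replace the permissive wording in SAP 2.2.2 with one fixed, symmetric rule for the main OS analysis. Either of these works:

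- **Censor all withdrawn patients** at the last contact before withdrawal, and use no register deaths; or
- **Use register vital status both ways**, only where a permitted register positively confirms vital status or is known to be complete. Deaths are events. Patients confirmed alive are censored at the earlier of the confirmation date and the cut-off, and that date is added as a source in Table 2.1-2. Where status cannot be confirmed this way, use neither deaths nor alive status and censor at the last contact before withdrawal.

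Do not treat the absence of a recorded death as proof of life unless the register is known to be complete. Present the alternative rule as a sensitivity analysis, and report withdrawals and register deaths by arm.

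The cost is a few lines of SAP text and, under the second option, one data source and a record of searches for patients found alive. Some register deaths may go unused in the main analysis. Censoring at withdrawal also assumes that withdrawal is unrelated to prognosis; if sicker patients withdraw, the second option is preferable where it is available.

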2.2.3 Subgroup of interest

Subgroup analyses will be performed for efficacy and safety as outlined below.

Efficacy

The primary efficacy and key secondary endpoints will be summarized by the following subgroups to examine the homogeneity of treatment effect provided that the primary efficacy analysis, and, key secondary analysis, based on the FAS are statistically significant:

- Tumor grade: G2 vs. G3 per eCRF
- Tumor origin: pNET vs. other origin per eCRF
- Small intestine as primary site of cancer (a subset of other origin per eCRF)
- Age category (<65 years vs. ≥ 65 years)
- Sex (Female vs. Male)
- Race (White vs. Asian)
- Tumor burden at baseline (Limited vs. Moderate vs. Extensive)

- Chromogranin A (CgA) prior to randomization ($\leq 2\times\text{ULN}$ vs. $> 2\times\text{ULN}$)
- SSTR highest tumor uptake score as per central assessment (Grade 3 vs. Grade 4)

So, if the primary efficacy endpoint is significant, the above applies to that endpoint. If a key secondary endpoint is significant, the above applies to that endpoint.

No formal statistical test of hypotheses will be performed for the subgroups, only point estimate of the treatment effect and 95%-confidence intervals will be provided (see [Section 2.5.6](#) for further analysis details). The objective of the efficacy subgroup analysis is to demonstrate homogeneity of treatment effect in the above subgroups.

Safety

Safety subgroup analyses will use the same method as for the analysis in the overall analysis set. Key safety analyses (deaths and SAEs) will be repeated on safety set in the following subgroups:

- Age category (<65 years vs. ≥ 65 years)
- Sex (Female vs. Male)
- Race (White vs. Asian)
- Creatine clearance at baseline (<60 mL/min vs. ≥ 60 mL/min)

The objective for carrying out these subgroup analyses is to identify potential safety issues that may be limited to a subgroup of patients, or safety issues that are more commonly observed in a subgroup of patients.

Summary tables will only be performed if at least 10% of patients or 10 patients are present in each subgroup. Some grouping of classes will be considered if necessary to obtain a sufficient number of observations.

2.3 Patient disposition, demographics and other baseline characteristics

The Full Analysis Set (FAS) will be used for all baseline and demographic summaries and listings unless otherwise specified. Summaries will be reported by treatment arm and for all patients and listings will be reported by treatment arm to assess baseline comparability. No inferential statistics will be provided. Demographic and baseline characteristics will also be summarized for patients who cross over to Lutathera or are re-treated with Lutathera, separately, unless otherwise specified.

Basic demographic and background data

All demographic and baseline disease characteristics data will be summarized and listed by treatment arm. Categorical data (e.g., gender, race, ethnicity, Karnofsky performance score as categorical) will be summarized by frequency counts and percentages; the number and percentage of patients with missing data will be provided. Those with Asian race will be further

broken down by Chinese, Indian, Japanese, Korean, or Vietnamese. Those with multiple races will be included in Other category. Continuous data (e.g., age, weight, height, body mass index) will be summarized by descriptive statistics (N, mean, median, standard deviation, Q1, Q3, minimum and maximum). Separate summaries will be prepared for patients who cross over to Lutathera or are re-treated with Lutathera.

Baseline stratification factors

The number (%) of patients in each randomization stratum based on data obtained from the IRT system will be summarized overall and by treatment arm for the FAS.

Diagnosis and extent of cancer

Summary statistics will be tabulated for diagnosis and extent of cancer. This analysis will include the following: primary site of cancer, presence of metastases, site of metastases, histopathology grade at diagnosis, time since initial diagnosis, presence/absence of target and non-target lesions, number and type of metastatic sites involved, ki67, highest SSTR tumor uptake score (based on cancer diagnosis page), extent of overall tumor burden, and, TNM criteria at diagnosis. Note: Presence/absence of target and non-target lesions will be based on the central laboratory report on RECIST target/non-target lesion assessment. Metastatic sites will be based on GEP-NET diagnosis page. Separate summaries will be prepared for patients who cross over to Lutathera or are re-treated with Lutathera.

To further characterize primary site of cancer, primary site locations will be grouped into three categories: pNET, small intestine and other by clinical review. The details of grouping will be covered in the programming specifications.

Medical history

Medical history and ongoing conditions, including cancer-related conditions and symptoms entered on (e) CRF will be summarized and listed by treatment arm. This will include Prior Antineoplastic Therapy (GEP-NET tumor procedures (including surgery and radiotherapy), and, GEP-NET tumor medication). Separate summaries will be presented for ongoing and historical medical conditions. The summaries will be presented by primary system organ class (SOC), preferred term (PT) and treatment arm. Medical history and current medical conditions will be coded using the Medical Dictionary for Regulatory Activities (MedDRA) terminology. The MedDRA version used for reporting will be specified in the CSR and as a footnote in the applicable tables/listings.

2.3.1 Patient disposition

Enrollment by country and center will be summarized for all screened patients and also by treatment arm using the FAS. The number (%) of randomized patients included in the FAS will be presented overall and by treatment group. The number (%) of screened and not-randomized patients and the reasons for screening failure will also be displayed. The number (%) of patients in the FAS who are still on treatment, who discontinued the study phases and the reason for discontinuation will be presented overall and by treatment group. Death due to COVID-19 will

be included in the display. Patient disposition will also be summarized for patients who cross over to Lutathera or are re-treated with Lutathera, separately, unless otherwise specified.

Protocol deviations

In this study, the term “major” protocol deviations corresponds to the term “important” protocol deviations.

The number (%) of patients in the FAS with any major protocol deviation will be tabulated by deviation category (as specified in the study Data Management Plan) overall and by treatment group for the FAS. Major protocol deviations related to Covid-19 will be tabulated separately overall and by treatment group. All protocol deviations will be listed.

Analysis sets

The number (%) of patients in each analysis set (defined in [Section 2.2](#)) will be summarized by treatment group and stratum.

2.4 Treatments (study treatment, rescue medication, concomitant therapies, compliance)

For details concerning rescue medication see Section 6.1 of the Protocol.

2.4.1 Study treatment / compliance

Duration of study treatment exposure, cumulative dose, number of doses, average duration of treatment cycles (for Lutathera only), dose intensity (DI) and relative dose intensity (RDI) will be summarized by treatment group. The number of participants with dose reductions/interruptions/modification and the reasons, will be summarized and listed. Details of the derivations and summaries are provided in the following sections. Participants with no exposure to the study treatment component will be excluded from the corresponding tabular summaries.

Categorical data will be summarized as frequencies and percentages. For continuous data, mean, standard deviation, median, 25th and 75th percentiles, minimum, and maximum will be presented.

The safety set will be used for all summaries and listings of study treatment.

2.4.1.1 Duration of exposure to study treatment

The duration of exposure to study treatment will be calculated as:

Duration of exposure to study treatment (days) = **(last date of exposure** to any treatment component) – (date of first administration of study treatment component) + 1

The duration of exposure to any single component of study treatment will be calculated as:

Duration of exposure (days) = (last day of exposure to study treatment component) – (date of first administration of study treatment component) + 1

The **last date of exposure** is defined as follows for the study treatment component:

- For Lutathera, the last date of exposure is defined as the last date of administration + 55 days
- For Octreotide LAR, the rules are the following:
 - For patients randomized in the investigational arm, if the last date of administration occurs after an administration of Lutathera, the last date of exposure is defined as the last date of administration for Octreotide + 55 days
 - For patients randomized in the investigational arm, if the last date of administration occurs after the 6-week washout period of the last dose of Lutathera (i.e., Octreotide starts the every 4 weeks schedule after discontinuation of Lutathera), then the last date of exposure is defined as the last date of administration + 27 days
 - For patients randomized in the control arm, the last date of exposure is defined as the last date of administration + 27 days

This duration of exposure includes the periods of temporary interruption (of any component of the study treatment for any reason). The duration of study treatment exposure and exposure to each treatment component will be summarized by treatment group and by treatment period. In addition, number of cycles and average duration of cycle (for Lutathera only) will also be summarized for single component of study treatment by treatment period.

For analyses related to the cross-over/re-treatment period, duration of exposure to Lutathera will be calculated as above during either the cross-over or re-treatment period as appropriate. Since administration of Octreotide LAR is optional in the re-treatment period (expected very few cases), the duration of exposure to Octreotide LAR will not be calculated for the re-treatment period.

